As with other underrepresented groups, it can be challenging to engage and retain individuals with MDD in clinical trials. Through a partnership with the University of Pennsylvania-led Randomized Evaluation of Trial Acceptability by INcentive (RETAIN) study, we will conduct a sub-study to test a financial incentive strategy designed to maximize recruitment and retention. The sub-study's innovative design will enable a definitive test

of how patients make research decisions in the face of money, and will provide the best possible evidence regarding the scientific and ethical pros and cons of incentives for research participation.

PARTICIPANT ELIGIBILITY

Target Population

Five hundred seventy-six males and females who smoke at least 1 cigarette per day, have a current or lifetime DSM-5 diagnosis of MDD without psychotic features (first episode of MDD can be prior to past two years) will be randomized to treatment. Two hundred and eighty-eight participants will be enrolled at Northwestern (lead clinical site) and 288 will be enrolled at the University of Pennsylvania (PENN). Randomization will be stratified by gender, severity of depressive symptoms (minimal/mild vs. moderate/severe), and clinical site (Northwestern, PENN).

Key Inclusion Criteria

Eligible participants will be males and females who:

1. Are 18 years of age or older and who report daily smoking of at least 1 cigarette per day.
2. Have been diagnosed with current or lifetime MDD without psychotic features according to the Diagnostic and Statistical Manual of Mental Disorders 5th Edition (DSM-5); Note: first episode MDD diagnosis date may be prior to the past two years.
3. Have or are willing to acquire a personal email address and access to the Internet, fax machine, PDF scanner, or camera phone for submission of therapy practice assignments;
4. Are able to speak, read, and write fluently in English.
5. Are able to provide written informed consent, which includes compliance with requirements and restrictions listed in the combined consent/HIPAA form.
6. Intend to reside in the geographic area for >8 months.

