Abstinence (primary outcome): Smoking will be assessed using a TLFB interview (Brown et al., 1998), and by breath carbon monoxide (CO) to verify self-report. Participants will be considered abstinent if they report abstinence (not even a puff of a cigarette) for ≥ 7 days prior to week 27 (24-weeks post-TQD) and have a CO ≤ 8 ppm at the time-point (Hughes et al., 2003). As per convention, participants are assumed to be smoking if they report smoking at the time-point, cannot be reached to provide data at the time-point, fail to provide a breath sample at the time-point, or provide a breath sample at the time-point that is > 8 ppm (Hughes et al., 2003). Daily smoking will be assessed at each session using the TLFB. The TLFB interview provides data that can be used to assess the timing and rates of lapses (smoking episodes not lasting 7 days), recovery events (return to abstinence), and relapse events, as well as to monitor changes in cigarettes smoked per day. These data will also be used to compute and assess secondary measures of smoking cessation (below). CO will be measured at each in-person visit to confirm smoking status. To obtain participants' CO value, the participant takes 3 deep breaths. On the third deep breath, participants are instructed to inhale and hold their breath for 10 seconds, then place their mouth securely around the disposable mouthpiece on the handheld CO monitor and to blow through the tube until they have completely expelled all of the air in their lungs.

Smoking behaviors (secondary outcome): CO-verified 7-day point prevalence abstinence at weeks 7 and 14 (4- and 10-weeks post-TQD, respectively) will be secondary measures. As per guidelines (Hughes et al., 2003), secondary outcomes at 24-weeks post-TQD will include: prolonged abstinence (relapse defined as 7 consecutive days of self-reported smoking after a 2-week grace period), continuous abstinence (no smoking between TQD and follow-up), and time to 7-day relapse (no grace period).

RETAIN Sub-Study Measures

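### Prolonged abstinence fails a participant only after 7 smoking days in a row and is not tied to CO, so steady smoking on 2 to 3 days a week would usually count as success

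*Combined protocol and SAP*

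**What the plan says.** The same definition appears under Outcome Assessments, under Outcomes Measures (Smoking behaviors) and under Data Analysis (Primary Aims 1-3): "prolonged abstinence (relapse defined as 7 consecutive days of self-reported smoking after a 2-week grace period". It is one of several measures introduced with "secondary outcomes at 24-weeks post-TQD will include". The others are continuous abstinence, which any smoking after the target quit day (TQD) breaks, and, in the wording of Outcomes Measures, "time to 7-day relapse (no grace period".

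Outcomes Measures (Abstinence) says that the TLFB can be used to assess "lapses (smoking episodes not lasting 7 days), recovery events (return to abstinence), and relapse events". An episode shorter than 7 days is therefore a lapse. No section limits how many lapses are allowed, counts total smoking days, or adds another route to relapse.

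On verification, the CO label among the secondary outcomes is attached to "CO-verified 7-day point prevalence abstinence at weeks 7 and 14". The limit of 8 ppm belongs to point-prevalence abstinence. CO is taken at in-person visits to confirm smoking status, but no text makes it part of prolonged abstinence. At Week 27 only self-reported abstainers are asked to come in for CO.

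**The concern.** A measure of prolonged abstinence should separate people who stay largely smoke-free from people who keep smoking. This rule detects only one pattern of failure, an unbroken week of smoking. Entrants must "report daily smoking of at least 1 cigarette per day", so moving to non-daily smoking is a possible result of treatment. The endpoint would score that as sustained quitting.

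The Background describes varenicline as reducing smoking reward and craving, and behavioral activation as replacing smoking with other rewards. If an active arm produced more reduction without cessation than its comparator, the prolonged-abstinence difference would be inflated. The documents give no figure for how often this happens in any arm. The direction is plausible; the size is unknown.

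**Working it through.** **Inputs from the plan.** Follow-up is 24 weeks after TQD. The grace period is 2 weeks. Failure is a run of 7 consecutive smoking days. Daily data come from the TLFB: "Daily smoking will be assessed at each session using the TLFB". The plan states no figure that depends on this rule, so there is none to reproduce.

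**Window.** 24 − 2 = 22 weeks; 22 × 7 = 154 days.

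**Regular pattern.** With k smoking days (k ≤ 6) and 7 − k smoke-free days repeating each week, grouped or not, no run exceeds k. The 7-day rule is never met. Smoking every weekend (k = 2) gives 2 × 22 = 44 smoking days and passes. At the limit, k = 6 gives 6 × 22 = 132 of 154 days and also passes, but only because the smoke-free day recurs without exception.

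**Irregular pattern (assumption: independent days, smoking probability p).** Let state i be the current run length, 0 to 6. Each day the process returns to state 0 with probability 1 − p or moves to i + 1 with probability p; reaching 7 is failure. The probability remaining in states 0 to 6 after 154 days is the chance of being counted as prolonged-abstinent under the plan's rule. The last column is the chance that a given 7-day window is smoke-free, (1 − p)^7, which the primary outcome needs before CO is even considered.

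| Average smoking days per week | p | Chance of no 7-day run in 154 days | Chance of a smoke-free 7-day window |
|---|---|---|---|
| 2 | 2/7 | 0.984 | 0.095 |
| 3 | 3/7 | 0.796 | 0.020 |
| 4 | 4/7 | 0.256 | 0.003 |
| 5 | 5/7 | 0.005 | <0.001 |
| 6 | 6/7 | about 0 | about 0 |

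Misclassification is therefore mainly at about 2 to 3 days a week. At 5 or 6 days a week it needs a rigidly regular diary.

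**Effect of a recurrent-smoking route.** Take as an example smoking on at least 1 day in each of 2 consecutive weeks. The chance that a week contains smoking is q = 1 − (1 − p)^7. The same recursion on weeks, with a run of 2 as failure over 22 weeks, gives:

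| p | q | Chance of passing the added rule |
|---|---|---|
| 0.05 | 0.302 | 0.195 |
| 0.10 | 0.522 | 0.007 |
| 2/7 | 0.905 | about 0 |
| 3/7 | 0.980 | about 0 |

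The added route removes the 2-to-3-day smoker. It also fails most people who smoke on only 5 to 10% of days.

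**The case against.** The strongest reply is that the plan has a graded set of measures and that prolonged abstinence is meant to be the lapse-tolerant one. The primary outcome and continuous abstinence both catch the persistent intermittent smoker. An arm that merely produced intermittent smoking would show up as disagreement between endpoints. This stands, and it limits the matter to a secondary endpoint. It does not make the label right: between a measure that one puff breaks and one that tolerates unlimited recurring lapses, the set has nothing that captures sustained quitting with limited slips.

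A second reply is that the definitions are given as following a cited guideline. Its text is not in the documents, so it settles nothing either way. By the same token, the documents do not establish any particular replacement threshold.

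Third, the absence of a CO requirement is silence, not a statement that CO is to be ignored. That is fair. All participants are asked for CO at Weeks 7 and 14, and the plan does not say whether a failed test overrides self-report here. The plan has to say which applies.

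A reader might go further in three ways that the documents do not support:

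- That someone smoking 6 days in 7 would typically be recorded as abstinent for 24 weeks. The window is 22 weeks, and with independent days the chance is about 0.
- That time to 7-day relapse is wrong. It times the event that it names; a person with no 7-day run has had no 7-day relapse. Redefining it would be a preference.
- That passing this endpoint while failing the primary outcome is a contradiction. Different definitions can give different results for one person.

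**Conclusion.** The concern holds for prolonged abstinence. Followed as written, the plan counts a person who keeps smoking 2 or 3 days a week as prolonged-abstinent with probability of about 98% or 80% if days are independent, and with certainty if smoke-free days are regular. Independence is an assumption. Smoking that clusters into longer runs would lower these chances, and regular spacing would raise them. Under the same assumption, a smoke-free final week, the first condition of the primary outcome, has a chance of only about 9% at 2 days a week and 2% at 3.

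The share of participants who would smoke in this way, and whether it differs by arm, cannot be obtained from the documents, so no bias in a treatment comparison is quantified. The primary outcome, the power statements and alpha do not depend on this definition. It is a cheap improvement, not an error that threatens the main conclusions.

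**What to change.** Make the change in the three places where prolonged abstinence is defined, and for that endpoint only:

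1. Add a second failure route for recurrent smoking after the grace period, derived from the TLFB. One example is smoking on at least 1 day in each of 2 consecutive weeks. The threshold is for the investigators to choose and justify before unblinding.
2. Require the CO-verified 7-day point-prevalence criterion at Week 27 to be met as well. State whether a failed CO test at Week 7 or 14 counts.
3. Keep the 7-consecutive-day rule as a sensitivity analysis, so that results under both rules are visible.
4. Leave time to 7-day relapse as named, and state that it is not to be read as time abstinent.

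**Cost.** Only wording and derivation code change, because the TLFB and Week 27 CO are already collected. The price is in the endpoint itself. Prolonged-abstinence rates will be lower. The measure moves closer to continuous abstinence and fails many light lapsers (pass chance about 20% at 5% of days and 0.7% at 10%, under independence). Table 2 has no smoking assessment between Weeks 14 and 27, so a weekly rule relies on recall of isolated smoking days over 27 − 14 = 13 weeks. A more tolerant threshold would ease the first two costs but not the third.

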Behavioral activation and varenicline for smoking cessation in depressed smokers

Principal Investigators: [name]. (Lead PI)
Northwestern University
[contact]

[name]. (Site PI)
University of Pennsylvania
[contact]

Biostatistician: [name].
Brown University
[contact]

Version Date: January 17, 2019

STUDY OBJECTIVES

The overall aim of this randomized controlled trial is to enroll and randomize 576 daily smokers with current or lifetime major depressive disorder (MDD) to receive 12 weeks of either: 1) Standard behavioral cessation treatment (ST) + varenicline; 2) Behavioral activation integrated with standard cessation treatment (BASC) + varenicline; 3) ST + placebo; or 4) BASC + placebo. Randomization will be stratified by gender, severity of depressive symptoms (minimal/mild vs. moderate/severe), and clinical site (Northwestern, PENN).

We will secondarily address mediators of treatment effects, as well as the effects of incentives on research participation.

The following aims and hypotheses will be tested:

Primary Aim 1: Compare behavioral activation for smoking cessation with standard cessation therapy for enhancing abstinence among smokers with current or lifetime major depressive disorder.

Hypothesis: BASC will increase bioverified 7-day point prevalence abstinence at 24-weeks post-quit versus ST among participants randomized to placebo.

Primary Aim 2: Compare varenicline with placebo for enhancing abstinence among smokers with current or lifetime MDD. Hypothesis: Varenicline will increase bioverified 7-day point prevalence abstinence at 24-weeks post-quit versus placebo among participants randomized to ST.

Primary Aim 2a: Compare varenicline with placebo on rate of adverse events (AE), including psychiatric and cardiovascular events, in smokers with current or lifetime MDD. Hypothesis: There will be no significant difference between conditions in AE rates.

Primary Aim 3: Compare BASC plus varenicline with ST plus varenicline, BASC plus placebo, and ST plus placebo for enhancing abstinence among smokers with current or lifetime MDD. Hypothesis: BASC plus varenicline will increase bioverified 7-day point prevalence abstinence at 24-weeks post-quit versus the other three conditions.

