7. Medical history and evaluation of vital signs and anthropometry to be completed by research staff.
8. A concomitant medication review, including antidepressant medication.
9. Once the above steps have been completed and if eligible at this point, the participant will complete baseline paper and pencil measures to assess: 1) variables that may serve as covariates and that allow for the assessment of antidepressant-varenicline interactions (antidepressant medication use and type) and external validity (e.g., demographics); 2) mediator variables (e.g., hedonic capacity); 3) psychiatric symptoms; and 4) smoking behavior.

10. If eligible, the participant will be randomized to treatment condition using a randomization scheme provided by [name] and implemented through the data management system. Randomization will be stratified by clinical site, gender, and severity of depressive symptoms (minimal/mild vs. moderate/severe, as defined using the BDI-II (Beck, Steer, & Brown, 1996)) and will be by permuted blocks of fixed size (18 participants per block) with unequal 4:4:5:5 allocation ratio across the four study arms, such that a minimum of N=128 participants be assigned to each psychological treatment group (BASC, ST) receiving placebo, while a minimum of N=160 participants be assigned to each psychological treatment group (BASC, ST) receiving varenicline.
11. Once randomized, participants are scheduled for the first treatment session (Pre-Quit, Week 1). There must be no more than two weeks between the intake session and the first treatment session.

At the baseline intake session, participants who are randomized for the RETAIN sub-study will complete the following additional procedures:

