Staff training will consist of a detailed explanation of the protocol and review of the CRFs. In addition, the duties of each research staffer will be outlined and all applicable regulations will be reviewed. Mock sessions with constructive critical feedback will be conducted. The MOP will be used for staff training and to guide procedures during the trial. Senior personnel will supervise junior staff and provide re-training as needed. Monitoring will be conducted in accordance with GCP and the U.S. Department of Health and Human Services Code of Federal Regulations Title 45, Part 46.a (<http://www.hhs.gov/ohrp/policy/ohrregulations.pdf>). Recruitment and enrollment will stop when 576 participants are consented, randomized and complete the study. On average, about 12 participants will be enrolled per month across the two study sites. Monitoring for AEs will be conducted in real-time by the study personnel and the site PI and study physician and psychologists. Research staff will complete thorough side effect assessments and send this information to the study physician and psychologists, who will determine the severity of the adverse events. The relationship of the event to the study drug and the course of action for the participant will be decided by the site physician and psychologists after reviewing the report. Participants will be monitored for the development of AEs by assessing side effects at each session between weeks 0 and 27 as well as through open-ended questions during assessments (at least 10 times during the trial). Monitoring may increase if required. Additionally, participants will be given a 24-hour emergency number they can call if necessary.

The PIs, study physicians, and psychologists will follow all participants who discontinue due to a serious AE until it resolves and becomes completely stable, unless a referral to another physician (i.e., specialist) is indicated or requested by the participant. All AEs and serious AEs will be documented in an Adverse Events CRF. This information will, in turn, be reported immediately to all necessary regulatory committees, including the FDA (see Data and Safety Monitoring Plan and Safety Monitoring and Reporting Protocol).

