To address hypotheses related to Aims 1-3, we base our estimates upon the Anthenelli et al. trial (2013) and the study by MacPherson et al (2010) that randomized 68 smokers with elevated depressive symptoms (BDI-II scores ≥ 10) but no current MDD to 8 weeks of treatment with either behavioral activation (BA) or standard behavioral treatment (BT). At 26-weeks post-TQD, bioverified 7-day point-prevalence abstinence rates were 14.3% for BA (n=35) and 0% for BT (n=33). In the Anthenelli et al. trial (2013), smokers with current or past (≤ 2 years) MDD received 12 weeks of varenicline or placebo. Bioverified 7-day point-prevalence abstinence rates at 24 weeks were 31.3% for varenicline (n=256) and 18.2% for placebo (n=269). Based upon our conceptual model of the therapeutic targets of BASC and varenicline individually, we predict that there will be a synergistic effect of combination treatment with BASC and varenicline on abstinence (see Figure 2). Assumed 7-day point prevalence abstinence rates at 24-weeks post-TQD in our 2x2 design are presented in Table 3, under an ITT approach that considers participants lost to follow-up as treatment failures. A minimum of N=128 participants be assigned to each psychological treatment group (BASC, ST) receiving placebo, while a minimum of N=160 participants be assigned to each psychological treatment group (BASC, ST) receiving varenicline.

Such a sample configuration (N=576 total) guarantees at least 85% power for testing each of the three pairwise comparisons of interest in Primary Aim 3: BASC + varenicline vs. ST + varenicline (42% vs. 24% abstinence, power = 85%), BASC + varenicline vs. BASC + placebo (42% vs. 18% abstinence, power = 98%), and BASC + varenicline vs. ST + placebo (42% vs. 5% abstinence, power > 99%) at a multiplicity-adjusted significance level $\alpha = .053 = .0167$.

This equates to enrolling about 12 participants per month (6/month/site) over the 48 month recruitment period. Further, it guarantees 91% power for testing the efficacy of BASC vs. ST (18% vs. 5% abstinence) among the

		Psychological Treatment	
		ST	BASC
Pharmacological Treatment	Placebo	5%	18%
	Varenicline	24%	42%

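### The rule for ending recruitment counts 576 participants who complete the study, while the rest of the plan sets 576 as the number randomised

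*Combined protocol and SAP*

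**What the plan says.** The Data and Safety Monitoring section, in its paragraph on staff training and monitoring, states: "Recruitment and enrollment will stop when 576 participants are consented, randomized and complete the study". The three conditions are cumulative, so a randomised participant who drops out does not count. No other sentence says when recruitment ends on reaching a target (the DSMB may separately recommend suspension). Study completion is not defined.

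Elsewhere the same number has a different meaning:

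- **Study Objectives:** "The overall aim of this randomized controlled trial is to enroll and randomize 576 daily smokers".
- **Target Population:** "Two hundred and eighty-eight participants will be enrolled at Northwestern (lead clinical site) and 288 will be enrolled at the University of Pennsylvania".
- **Power, arm sizes:** "A minimum of N=128 participants be assigned to each psychological treatment group (BASC, ST) receiving placebo", and "a minimum of N=160 participants be assigned to each psychological treatment group (BASC, ST) receiving varenicline".
- **Baseline Intake Session:** the same minimums, delivered by "permuted blocks of fixed size (18 participants per block) with unequal 4:4:5:5 allocation ratio".
- **Power, accrual:** "This equates to enrolling about 12 participants per month (6/month/site) over the 48 month recruitment period". The sentence directly after the stopping rule repeats the rate of about 12 per month.
- **Power and Missing Data Approaches:** the assumed abstinence rates, and the primary analysis, treat anyone lost to follow-up as a failure and keep every randomised participant in the denominator.
- **Participant Recruitment:** withdrawal is expected to be at most 20%, and more than 70% are expected to complete follow-up. Missing Data Approaches also gives at least 70% reached at 24 weeks.

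**The concern.** With any appreciable dropout, 576 cannot be both the number randomised and the number who complete. On the plan's own retention figures the two counts differ, and the sentence that staff would act on to close accrual uses the one that nothing else in the plan is built on.

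At stake is a fixed planned size. Under the literal rule the final number depends on observed retention and on how someone chooses to define completion. That could mean the end of treatment at Week 14, the Week 27 phone assessment, or the Week 27 clinic visit, which only self-reported abstainers are asked to attend. The 288-per-site targets and the 48-month period would no longer apply, and more people than planned would be randomised, some to placebo, for no stated purpose. The DSMB is asked to review recruitment against goal and needs one goal. Secondary Aim 2b (cost-effectiveness of incentives) also presumes that the size to be recruited is fixed.

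**Working it through.** **1. What 576 counts in the design.**

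- Arms: 2 × 128 + 2 × 160 = 576.
- Blocks: 576 / 18 = 32; 32 × 4 = 128 and 32 × 5 = 160.
- Sites: 2 × 288 = 576.
- Accrual: 12 × 48 = 576.

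**2. The plan's power figures.** Two-sided test of two proportions, pooled variance, no continuity correction:

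power = Φ[(|p1 − p2| − z × SE0) / SE1], with SE0 = √[p̄(1 − p̄)(1/n1 + 1/n2)] and SE1 = √[p1(1 − p1)/n1 + p2(1 − p2)/n2].

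For 42% vs 24% with 160 per arm and α = 0.05/3: SE0 = 0.0526, SE1 = 0.0516, z = 2.394. Power = Φ[(0.18 − 0.1259)/0.0516] = 85.3%.

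| Comparison | n | Stated | All 576 in denominators | 80% of them | 70% of them |
|---|---|---|---|---|---|
| Aim 3, 42% vs 24% | 160/160 | 85% | 85.3% | 75.2% | 68.4% |
| Aim 3, 42% vs 18% | 160/128 | 98% | 98.2% | 94.6% | 90.9% |
| Aim 3, 42% vs 5% | 160/128 | >99% | >99.9% | >99.9% | >99.9% |
| Aim 1, 18% vs 5% | 128/128 | 91% | 90.8% | 83.6% | 78.3% |
| Aim 2, 24% vs 5% | 160/128 | >99% | 99.7% | 98.6% | 97.3% |

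The stated figures reproduce with 576 in the denominators. By itself this shows only that 576 is the number analysed. The statement in the same section that losses count as failures makes the number analysed equal to the number randomised. Attrition is therefore already inside the assumed abstinence rates.

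**3. Number randomised under the literal rule, dropout alone.** N = 576 / (1 − d), where d is the proportion not completing; months = N / 12.

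- d = 0.10 (illustrative): 640, +11%, 53 months.
- d = 0.20 (withdrawal limit): 720, +144 or +25%, 60 months.
- d = 0.30 (follow-up limit): 823, +247 or +43%, 68.6 months.

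**4. Lag to completion.** The primary endpoint is at Week 27. If completion means reaching it, accrual stays open about 27 / 4.345 = 6.2 months after enough people have been enrolled. At a constant 12 per month that adds 6.2 × 12 ≈ 75 people. Totals become about 651 (+13%) with no dropout, 795 (+38%) at 20% and 897 (+56%) at 30%.

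**5. Effect on power.** With the assumed rates held fixed, the 85% comparison would have 92.8% power at 720 randomised (200 per varenicline arm) and 95.8% at 823 (about 229 per arm).

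**The case against.** The strongest reply is that the sentence is loose drafting. It sits in a training and monitoring paragraph rather than the design or statistics section, the next sentence repeats the accrual rate that yields 576 enrolled, and the objectives, population, power and analysis sections agree with one another. That is probably the right account of how the wording arose. It does not remove the conflict, because a rule for closing recruitment has to be workable as written.

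Three stronger inferences are tempting, and the documents do not support them.

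- **That the planned arm sizes would be broken.** 128 and 160 are stated as minimums. A larger trial in the same blocks exceeds them and keeps the ratio: 720 is 40 blocks, giving 160/160/200/200.
- **That the trial will over-enrol by 25% to 43%.** Those values come from limits on two different quantities, withdrawal and completion of follow-up. On dropout alone they are ceilings for two readings of completion, and they leave out the lag, which pushes the other way. They are not a forecast.
- **That validity suffers.** Power would rise, and a sample size that depends on overall retention is not shown to bias the comparison of all randomised participants.

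One further point stands. It would be too broad to say that nothing in the plan could use a completer target. For Secondary Aim 1 the Power section compares a requirement of 562 with 576 and makes no allowance for missing mediator or outcome data. The plan does not, however, offer this as a reason for the stopping rule.

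**Conclusion.** Wrong as written. The only target-based rule for ending recruitment counts completers, and it cannot be reconciled with a plan that sets 576 as the number randomised and expects some of them to be lost.

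On dropout alone, the literal rule would randomise up to about 720 at the 20% withdrawal limit or up to about 823 at the 70% follow-up limit, with about 75 more from the wait for the last completers. These sizes rest on the plan's retention limits, a constant 12 per month, and completion taken as reaching Week 27 about 27 weeks after intake. Better retention gives smaller numbers.

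The 288-per-site targets, the 48-month period and the planned number exposed would not hold. Power, the arm minimums and the validity of the primary comparison are not threatened. The inconsistency concerns an operating rule and should be corrected, but it does not undermine the design.

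**What to change.** Replace the sentence in Data and Safety Monitoring with one that drops the completion condition, for example: *Accrual closes once 576 participants have given consent and been randomised.* This agrees with the objectives, site targets, arm sizes, accrual rate and primary analysis. It leaves every stated power figure unchanged and costs one sentence.

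If a completer target was really intended, the sponsor should say why, define completion by a named visit or assessment, and restate the number to be randomised, the site targets and the recruitment period to match. That is a re-planning exercise, with the larger numbers shown above.

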Data Analysis

Preliminary analyses will assess sample characteristics by treatment with chi-square or logistic regression (tobacco dependence, use of antidepressant medication, number of past depressive episodes, and number of other Axis I disorders). These variables will also be examined for their relationship to completion of outcome assessments. Variables related to treatment arm and completion of follow-ups will be included as covariates in analyses of study aims. Treatment compliance measures (psychological treatment sessions, medication) will be evaluated across treatment arms, and controlled for in primary analyses.

Primary Aims 1-3: Outcome Analyses

[figure not shown]
The primary outcomes will be 7-day point prevalence abstinence at week 27 (24-weeks post-TQD; self-reported abstinence for 7 days prior to the assessment and breath CO \leq 8 ppm) and AE rates. CO-verified 7-day point prevalence abstinence at weeks 7 and 14 (4- and 10-weeks post-TQD, respectively) will be secondary measures. As per guidelines (Hughes et al., 2003), secondary outcomes at 24-weeks post-TQD will include: prolonged abstinence (relapse defined as 7 consecutive days of self-reported smoking after a 2-week grace period), continuous abstinence (no smoking between TQD and follow-up), and time to 7-day relapse. Other than time to relapse, all outcomes of interest are binary (abstinence and AE rates) and will be analyzed using logistic regression. The effect of varenicline on AE rates (Primary Aim 2a) will be based upon the union-intersection test arm for establishing non-inferiority in the proportion of participants experiencing moderate to severe AEs in the varenicline vs. the placebo arm (Hauschke et al., 1999). To ensure that tests on the overall sample do not mask differential effects by antidepressant medication use and type, these analyses will be preceded by a Breslow-Day for homogeneity across strata of interest. If no evidence of heterogeneity is found, stratum-specific estimates will be combined using a Cochran-Mantel-Haenszel weighing scheme (Wiens & Heyse, 2003).

Missing Data Approaches

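### The analysis section gives no multiplicity rule for the three Aim 3 comparisons; writing in Holm keeps the 5% family-wise bound and lifts power against ST + varenicline from about 85% to about 93%

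*Combined protocol and SAP*

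**What the plan says.** Under Study Objectives, the Aim 3 hypothesis is that "BASC plus varenicline will increase bioverified 7-day point prevalence abstinence at 24-weeks post-quit versus the other three conditions". Statistical Considerations, Power, treats this as three separate pairwise comparisons and states that the design "guarantees at least 85% power for testing each of the three pairwise comparisons of interest in Primary Aim 3". It gives 85% against ST + varenicline (42% vs 24%), 98% against BASC + placebo (42% vs 18%) and, against ST + placebo (42% vs 5%), "power > 99%) at a multiplicity-adjusted significance level" of 0.0167. That is 0.05 divided by 3; the slash is lost in the text version.

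Data Analysis, Primary Aims 1-3: Outcome Analyses, says that apart from time to relapse "all outcomes of interest are binary (abstinence and AE rates) and will be analyzed using logistic regression". Neither this section nor Missing Data Approaches states a significance level, an adjustment method or a testing order for Aim 3. Aims 1 and 2 are each set at 0.05 in the Power section. The only multiplicity procedure named in the document is Sidak-Holm, and it applies to the RETAIN sub-study alone.

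**The concern.** The rule that decides a primary aim appears only as an input to a power calculation. It should stand in the analysis section, fixed before anyone sees outcomes by arm.

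If the rule is simply carried over as a flat 0.0167, the plan also gives up power for nothing. The comparison with ST + varenicline asks whether behavioral activation adds to varenicline, and it has the lowest stated power of the three. Under the plan's own rates the other two are near-certain rejections. A step-down rule would then usually test this comparison at 0.05, with the same family-wise guarantee and no extra participants.

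**Working it through.** **Inputs (Power section).** n = 160 in each varenicline arm and 128 in each placebo arm. Assumed abstinence: BASC + varenicline 42%, ST + varenicline 24%, BASC + placebo 18%, ST + placebo 5%. Participants lost to follow-up count as failures, so the rates apply to the full n. Sidedness is not stated for Aim 3; two-sided is inferred because it reproduces the stated powers (one-sided gives 90.7% for the first comparison).

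**Reproducing the plan.** Power = Φ[(d − z·SE0)/SE1], where SE0 is the pooled standard error and SE1 the unpooled one. For 42% vs 24%:

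- d = 0.18 and the pooled rate is 0.33
- SE0 = √(0.33 × 0.67 × 2/160) = 0.0526
- SE1 = √[(0.42 × 0.58 + 0.24 × 0.76)/160] = 0.0516
- At 0.0167 two-sided, z = 2.394: Φ[(0.18 − 2.394 × 0.0526)/0.0516] = Φ(1.05) = 85.3% (stated 85%)

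The same formula gives 98.2% for 42% vs 18% (stated 98%) and above 99.9% for 42% vs 5% (stated above 99%). All three reproduce.

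**Holm.** Order the three p-values. Compare the smallest with 0.05/3 = 0.0167, the next with 0.05/2 = 0.025 and the largest with 0.05, stopping at the first failure. Once the two placebo comparisons are rejected, ST + varenicline is tested at 0.05. There the formula gives Φ[(0.18 − 1.960 × 0.0526)/0.0516] = Φ(1.49) = 93.2%, which is the ceiling for Holm on this comparison.

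**Joint calculation.** The three tests share the BASC + varenicline arm, so the Holm figure needs the joint distribution. It was enumerated exactly: condition on the shared arm's count, sum over the independent binomial counts of the other arms, and apply two-sided pooled chi-square tests. A simulation of 1,000,000 trials agreed within 0.1 points. Power for BASC + varenicline vs ST + varenicline, with rates in the order BASC+var / ST+var / BASC+pbo / ST+pbo:

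| Rates (%) | Flat 0.0167 | Holm |
|---|---|---|
| 42 / 24 / 18 / 5 (plan) | 85.5% | 93.2% |
| 42 / 24 / 18 / 18.2 | 85.5% | 93.0% |
| 42 / 24 / 30 / 18.2 | 85.5% | 89.5% |
| 38 / 24 / 18 / 5 | 62.8% | 77.0% |
| 38 / 24 / 30 / 18.2 | 62.8% | 68.8% |
| 42 / 31.3 / 18 / 18.2 | 34.5% | 51.2% |
| 42 / 31.3 / 30 / 18.2 | 34.5% | 44.8% |

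The 31.3% and 18.2% come from the earlier varenicline trial cited in the Power section ("abstinence rates at 24 weeks were 31.3% for varenicline (n=256) and 18.2% for placebo (n=269"). The 30% and 38% are illustrative assumptions.

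Power to win all three comparisons rises from 84.7% to 92.9% at the plan's rates, and from 36.4% to 54.2% at 42/24/30/18.2. With a continuity correction, the plan-rate figures for the first comparison are 82.4% flat and 91.4% Holm.

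**Error rates.** With 24% in every arm, the family-wise error is 4.5% under both rules. If only the ST + varenicline null is true (42/42/18/5), the false-positive risk on it is 1.6% flat and 4.7% Holm. Over eight full and partial null configurations, Holm's family-wise error was at most 4.9%.

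**The case against.** - **The rule is already there.** A flat 0.05/3 for each of three comparisons is Bonferroni in all but name, and it sits in the same chapter. That is fair: the intent can be read and the level is valid. But it is stated only as a power input, and a uniformly more powerful rule is available.
- **The 5% bound is local.** It covers only the three Aim 3 comparisons. Aims 1 and 2 are each tested at 0.05 outside this family. This stands, and it is equally true of the flat rule.
- **Aim 3 might require all three wins.** Each test could then run at 0.05 unadjusted and Holm would be unnecessary. The hypothesis wording allows that reading, but powering each comparison at an adjusted level contradicts it. Little hangs on it: all-three power at 0.05 each is 93.0% at the plan's rates and 54.7% at 42/24/30/18.2, against Holm's 92.9% and 54.2%.
- **The 93% is conditional.** It assumes the plan's rates and an unadjusted chi-square, whereas the plan specifies logistic regression with covariates. The plan's 85% has the same limits. The largest sensitivity is the ST + varenicline rate: at 31.3%, Holm reaches only 51.2%. Any revised power statement should say so.
- **Timing.** Accrual has begun, and the study biostatistician presents unblinded side-effect data to the DSMB, whose report items also include efficacy. Relaxing a primary threshold mid-trial therefore needs a documented safeguard. This is a reason for care, not for leaving the rule unwritten.

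**Conclusion.** The point holds as an efficiency gain and a gap in specification, not as an error. The plan's powers are right and a flat 0.0167 would be valid. Under the assumed rates, Holm cuts the chance of missing a true BASC + varenicline advantage over ST + varenicline from 14.5% to 6.8%, about half. The size of the gain rests on two-sided tests, the planned arm sizes and large effects against both placebo arms. As those effects shrink, Holm's power falls towards the flat figure but never below it.

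**What to change.** In Primary Aims 1-3: Outcome Analyses, state that the three Aim 3 comparisons are separate two-sided claims tested by Holm's step-down procedure (0.0167, 0.025, 0.05), and that the 5% family-wise bound covers these three only. Date the change before unblinding, and record that those deciding it had not seen abstinence by arm.

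In the Power section, keep 85%, 98% and above 99% as the conservative floor. Add that, under the assumed rates, Holm gives about 93% against ST + varenicline and about 93% for all three. Say that the first figure falls to about 89% if the placebo arms reach 30% (illustrative) and 18.2%, and to about 51% if ST + varenicline reaches the cited 31.3% with placebo arms at 18% and 18.2%.

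The cost is a sentence or two in each section and no change in sample size. There are two downsides. Holm uses more of the 5% allowance when some nulls are false, and its simultaneous confidence intervals are less simple. Unadjusted 95% intervals, labelled as such, can be reported beside Holm-adjusted p-values.
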